### **Accounting for versions of Actissist**

Digital interventions are characterised by the iterative changes to the interventions during the life of a trial. As the app is updated to a new version, participants in the Actissist arm will receive a newer version of the app if they are recruited later in the study. ClinTouch remained unchanged during the duration of the study. For the intention-to-treat analysis, we ignore the version of the app and compare Actissist versus ClinTouch based on random assignment. Therefore, this analysis necessarily averages over different versions of the intervention.

Since the app version is only available in the intervention arm of the trial, simple covariate adjustment for app-version is not recommended. Instead, we consider categorical time periods during recruitment to the study, which serves as a proxy for the version of the Actissist app that was available at the time of randomisation. This indicates the version of the Actissist app that participants randomised to the Actissist arm received, and the version that the ClinTouch arm would have received had they been randomised differently. This is measured at baseline in all participants regardless of subsequent random assignment.

As a subgroup analysis, we will repeat the primary analysis in subgroups defined by each time period of recruitment. We will test if the treatment effect is equal across time periods, and interpret differences to be indicative of the version of the app available at that time period.

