#### Sample size

The planned sample size was 170 participants recruited over 19 months. 63 per group will give 80% power to detect an effect size of 0.4 (6 points on the PANSS with an SD of 15), based on a two-group t-test with a 0.05 two-sided significance level, assuming a baseline-endpoint correlation of 0.6. Allowing 20% loss to follow-up, in order to maintain 80% power, we will recruit 85 patients per group (N=170). The SD, correlation and attrition rate are based on figures from Actissist 1.0.

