### Randomisation procedure, allocation concealment

The randomisation process is conducted by a remote internet-based randomisation service (www.sealedenvelope.com). The allocation sequence will be developed using a computer random number generator to allocate participants on a 1:1 ratio, stratified by service (early intervention vs community mental health).

The randomisation list will be kept by the remote randomisation service (www.sealedenvelope.com) and kept separate to the collection of outcomes on the study database. The randomisation list will only be revealed to the researchers once all the recruitment is completed.

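### The SAP commits in advance to reading differences in effect between recruitment periods as app-version differences, although version cannot be separated from other effect modifiers that changed over recruitment and the test has low power

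*SAP*

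**What the plan says.** The section Accounting for versions of Actissist explains that the app was updated during the trial, that later recruits to the Actissist arm received newer versions, and that ClinTouch did not change. The intention-to-treat comparison ignores version and averages over it. Because version exists in one arm only, the SAP uses categorical periods of recruitment, defined for both arms at baseline, as a proxy for the version available at randomisation.

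It then states that "we will repeat the primary analysis in subgroups defined by each time period of recruitment", that equality of the treatment effect across periods will be tested, and that the team will "interpret differences to be indicative of the version of the app available at that time period".

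The section gives no number of periods, cut-points or sizes. It does not call the analysis exploratory, names no other explanation for a difference, and does not say how a non-significant test will be read. The Version history shows that this analysis was added in version 0.5 (22/06/2020). The COVID-19 section says that recruitment had already ended by March 2020.

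**The concern.** The last clause fixes an interpretation before the data are seen. Randomisation protects Actissist versus ClinTouch within a period; it does not protect the comparison of that contrast between periods. Version follows calendar time by construction, so a treatment-by-period difference has at least two possible sources: the version, and any other effect modifier whose distribution changed over the planned 19 months of recruitment.

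Service mix shows how this could happen. Service enters the model as a main effect only (section 5, Analysis of primary and secondary outcomes, and Appendix 1). If the effect differed between early intervention and community services, and the balance of recruitment between them shifted, a period difference would appear with no version effect at all. The SAP does not say that such a shift occurred; the point is that its analysis could not distinguish it from a version effect.

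At stake is a statement about which version of a digital intervention works better, resting on a comparison that was not randomised and is imprecise.

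**Working it through.** **Inputs from the SAP, Sample size.** The calculation is "based on a two-group t-test with a 0.05 two-sided significance level"; the target is "6 points on the PANSS with an SD of 15", "assuming a baseline-endpoint correlation of 0.6". Planned recruitment is 170 with 20% loss, so 170 × 0.8 = 136 with data.

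**The plan's own figure.** The SAP says "63 per group will give 80% power to detect an effect size of 0.4".
- Baseline-adjusted SD: 15 × √(1 − 0.6²) = 12.
- n per group: 2 × (1.960 + 0.842)² × 12² / 6² = 62.8, so 63. Power at 63 is 80.1% by the normal approximation. The figure reproduces.

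**Assumptions not in the SAP.** There are K = 2, 3 or 4 equal periods, and the true effect differs between periods by 6 points. Six points is the SAP's target for the main effect, borrowed here as a yardstick.

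**Contrast of two periods, 136 analysed.** The variance of one period's effect is v = 4 × 12² / (136/K). The SE of the difference between two periods is √(2v). Power is Φ(6/SE − 1.96), and the difference detectable with 80% power is 2.80 × SE.

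| Periods | SE, one period | SE, difference | Power for 6 points | 80% power needs |
|---|---|---|---|---|
| 2 | 2.91 | 4.12 | 30.8% | 11.5 points |
| 3 | 3.56 | 5.04 | 22.1% | 14.1 points |
| 4 | 4.12 | 5.82 | 17.6% | 16.3 points |

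**Test of equality across all periods.** This is closer to what the SAP describes. Power comes from a noncentral F with K − 1 and 136 − 2K − 1 degrees of freedom and noncentrality Σ(δₖ − mean δ)²/v. For K above 2 the lower figure takes effects evenly spaced from 0 to 6, and the higher takes one period differing from the rest by 6.
- 2 periods: 30.4%
- 3 periods: 16.8% to 21.1%
- 4 periods: 12.6% to 15.6%

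Across both tests the range is about 13% to 31%.

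**Sensitivity of the two-period contrast.**
- 126 analysed (63 per group): 28.9%, 20.8% and 16.7% for 2, 3 and 4 equal periods.
- All 170 analysed: 37.1%, 26.5% and 21.0%.
- Two periods split 80/20, 136 analysed: 21.4%.
- Two equal periods, 136 analysed, other differences: 10.9% for 3 points, 59.0% for 9 points, 83.0% for 12 points.

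**Separate subgroup fits.** With two equal periods and a true effect of 6 points in both, each fit has 54% power. The chance that exactly one is significant is 2 × 0.54 × 0.46 = 0.50. Comparing subgroup p-values would thus suggest a difference about half the time when there is none, so the reading should rest on the interaction.

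**The case against.** The strongest reply is that the design is better than a before-and-after comparison. Every period has a concurrent randomised control on an unchanged app, so changes in season, staff, usual care or assessment that move both arms equally drop out. This stands. A reader might infer that period is confounded with everything that changed during recruitment. It is not: only changes that modify the Actissist-versus-ClinTouch difference compete with version. Nor does the SAP show that any such factor changed; version is the one change it documents.

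The wording is also hedged: the SAP speaks of a proxy, of differences being indicative, and of a subgroup analysis. That lowers the stakes, but neither term tells the reader that another explanation exists.

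Three further inferences are not supported:
- That the test has one definite power, such as 22%. That figure belongs to three equal periods, 136 analysed and a two-period contrast. The SAP fixes none of these and claims no power for this test.
- That the SAP will read a null result as equal versions. It states no rule for a null result; the gap is only that it does not rule this reading out.
- That pandemic changes distort the 12-week comparison. The COVID-19 section says all 12-week follow-ups were complete by March 2020 and that only the 24-week data of 21 participants could be affected.

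Finally, the SAP already commits to a test of equality, and its definition of the periods largely implies cutting at release dates. The modelling part of the fix is therefore a clarification.

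**Conclusion.** The concern holds in a limited form. The SAP pre-commits to an attribution that its design cannot establish by itself: a difference in effect between periods may come from version or from another effect modifier that drifted over recruitment, and the analysis cannot separate them. It would go too far to say that differences can never be discussed in terms of version; version is a legitimate candidate explanation, but not the only one.

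Power for a 6-point difference is roughly 13% to 31% under two to four equal periods, 136 analysed, SD 15 and correlation 0.6. Two equal periods need about 11.5 points for 80% power, almost twice the 6-point target for the whole treatment effect. A non-significant result would say little about whether versions differ. The number, size and balance of the periods are assumptions. Fewer losses raise the figures somewhat (37% at best in the cases tried), and unequal periods lower them.

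The primary intention-to-treat result does not depend on this analysis, so the point is secondary. It is still worth correcting, because it changes what the trial may conclude at almost no cost.

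**What to change.** Replace the attribution clause with:

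> This analysis is exploratory. Differences between periods may reflect the app version or other effect modifiers that changed during recruitment, and cannot by themselves be attributed to version; a non-significant test will not be read as showing equal effects.

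State how the equality test is done: one model with all participants, adding period, treatment-by-period and their interactions with timepoint, and testing the treatment-by-period interaction at 12 weeks. Cut the periods at the app release dates and list them; every version given at randomisation already existed when this analysis was added. Report the interaction estimates with 95% confidence intervals. Period-specific effects can be shown beside them.

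The cost is a few sentences and one model. The downside is a weaker statement about versions.

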## Appendix 1 Example analysis code

Data will be in long format with two rows for each participant, one for 12 week time point and one row for the 24 week timepoint.

#### Variable names

- pid: participant id
- treat: Arm of the trial participant is randomised to
- timepoint: follow-up timepoint
- baseline: baseline measure of the outcome
- service: Stratification factor
- outcome: outcome measure

#### Analysis code

\*Model for outcomes analysed using mixed effect model:

```
mixed outcome i.treat##i.timepoint baseline service || pid:, ///
res(unstructured, t(timepoint)) noconstant reml
margins treat, at(timepoint==12) pwcompare(effects)
```

\*Model for proportion of abstinent days from timeline follow back:

```
meglm outcome i.treat##i.timepoint baseline service || pid:, ///
res(unstructured, t(timepoint)) noconstant ///
family(binomial 30) link(identity)
```

\*\*End of treatment - should be the same as main effect of treat in above command

```
**Follow-up
```

```
margins treat, at(timepoint==24) pwcompare(effects)

//Should be the same as main effect of treat in:

// mixed outcome i.treat##ib24.timepoint baseline service || pid:, ///
res(unstructured, t(timepoint)) noconstant reml
```

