## 5. Statistical methods for inferential analysis

#### Analysis of primary and secondary outcomes

The primary and secondary outcomes, with the exception of the proportion of cannabis free days, will be analysed using a linear mixed-effects models with outcome measurement (at the two follow-up time points) as the dependant variable. The model will include fixed effects for timepoint, treatment, timepoint by treatment interactions, the baseline measure of the outcome, assuming a linear relationship between baseline and outcome, and service (2 categories: i) early intervention; ii) community mental health). Observations will be clustered by participant with an unstructured correlation matrix for the residuals. The model will be fitted using restricted maximum likelihood (19).

For each outcome and timepoint we will report the treatment effect estimate as the adjusted mean difference between groups, its standard error, 95% confidence intervals and p-value.

In addition, we will report estimates for Cohen's D effect sizes as the adjusted mean difference of the outcome divided by the sample standard deviation of the outcome at baseline. Confidence intervals for Cohen's D will be calculated by dividing the confidence limits by the sample standard deviation of the outcome at baseline. These will be displayed in a Forest Plot with the primary outcome at the top, followed by secondary outcomes.

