#### Time line follow back (TLFB)

Average weight per using day will be analysed using a linear mixed-effects model in the same way as other primary and secondary outcomes.

The proportion of cannabis free days will be analysed using a mixed effects generalised linear model, with family binomial and an identity link. The random and fixed parts of the model will be specified in the same way as the mixed effects model for other primary and secondary outcomes, including the baseline proportion of cannabis free days as a fixed effect.

Inferential analysis will only be conducted on outcomes from the TLFB separately for one month recall and three month recall (proportion of abstinent days and Average daily weight per cannabis using day).

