## Scoring rules for outcomes

Outcome acronym	Number of	Scoring	Min-Max	Scores for
Succome acronym	questions	Jeornig	possible	better
	questions		values	outcomes
PANSS total score	30 (7 +ve, 7 -	Sum of items	30-210	Lower
	ve, 16 general)			
PSYRATS - delusions	6	Sum of all items	0-24	Lower
PSYRATS - hallucination	11	Sum of all items	00-44	Lower
CDSS	9	Sum of items	0-27	Lower
PSP	4	Total score is entered directly into the database	1-100	Higher
PCPW – Perceived criticism	4	Mean of items	1-10	Lower
PCPW – Perceived warmth	3	Mean of items	1-10	Lower
QPR	15	Sum of the items	15-75	Higher
WEMWEBS	14	Sum of the items	14-70	Higher
ISMI	29	Mean of completed	1-4	Lower
		items reverse scoring items 7, 14, 24, 26 and 27		
AUDIT; past 3 months)	10	Sum of items	0-40	Lower
CUDIT-R; past 3 months.	8	Sum of items	0-32	Lower
ASSIST	71	Sum of items by substance.	0-31 tobacco 00-39 other drugs	Lower
DUDIT-e: Positive aspects	17	Sum of items	0-68	Higher scores more positive
DUDIT-e: Negative aspects	17	Sum of items	0-68	Higher scores more negative
DUDIT-e: Treatment 8 readiness		Sum of items excluding items 6 and 7 and reverse scoring items 1 and 9.	0-16	Higher scores more ready
TLFB – Proportion of days using cannabis*		Numerator: 30 – number of days abstinent Denominator: 30	0-1	Lower

TLFB - Average daily weight per cannabis using day*	2	Total weight/using days.  Total weight = number of units consumed.  Using days = (30 - number of days abstinent)  If using days = 0 outcome will be 0.	Non- negative	
ERS	28	Sum of the items. Reverse score items 10-18, and item 28.	28-112	Higher
QFQ - Ease of use	5	Qs 7, 8 (reversed), 11, 12 (reversed)	1-7	Lower
QFQ - Fit in daily life	5	Qs 3, 5, 6, 9, 10, and 21	1-7	Lower
QFQ - Acceptability	6	Qs 4, 15, 16, 17 (reversed), 20, 22 (reversed)	1-7	Lower
QFQ - Perceived helpfulness	4	Qs 13 (reversed), 14 (reversed), 18 and 19 (reversed)	1-7	Lower

\*One month recall data was collected using a 30 day period. For three month the time period was 90 days.

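### The TLFB cannabis-days outcome is scored as a 0–1 proportion but coded as binomial with 30 trials, and the SAP does not fix which scale is modelled or reported

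*SAP*

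**What the plan says.** - **Scoring (Appendix 2, Scoring rules for outcomes).** The entry for the cannabis-days outcome reads "Numerator: 30 – number of days abstinent Denominator: 30", with a listed range of 0–1. The footnote adds "For three month the time period was 90 days".
- **Model in the text (Section 5, Time line follow back).** "The proportion of cannabis free days will be analysed using a mixed effects generalised linear model, with family binomial and an identity link". The fixed part follows the other outcomes, "including the baseline proportion of cannabis free days as a fixed effect".
- **Code (Appendix 1).** The block is labelled as the model for the proportion of abstinent days. It fits `outcome` with "family(binomial 30) link(identity". The variable list gives only "outcome: outcome measure" and describes `baseline` as the baseline measure of that outcome.
- **Reporting (Section 5, Analysis of primary and secondary outcomes).** Each outcome gets an adjusted mean difference and a Cohen's d, the latter being "the adjusted mean difference of the outcome divided by the sample standard deviation of the outcome at baseline".

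**The concern.** A binomial model with 30 trials describes a number of days between 0 and 30. The SAP's scoring table, its Section 5 text and its code label all describe a number between 0 and 1. Because `baseline` is the same measure as `outcome`, and Section 5 states that the baseline is a proportion, the natural literal reading is that the dependent variable is a proportion too. A participant abstinent on half the days would then enter as 0.5 and be treated as half a day out of 30.

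At stake are the adjusted difference, its standard error and confidence interval, and the Cohen's d shown in the forest plot for this outcome.

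**Working it through.** **Inputs from the SAP.** Trials 30; identity link; outcome score (30 − days abstinent)/30; recall windows of 30 and 90 days.

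**Inputs assumed, not in the SAP.** A true difference in proportions of 0.10 (0.50 v 0.60); SD of the proportion 0.33, range 0.25 to 0.40; for one simulation, 25 users per arm.

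**1. The plan's own score.** With 30 abstinent days the score is 0/30 = 0; with none it is 30/30 = 1. The listed range of 0–1 is reproduced.

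**2. Coefficient if the 0–1 score is the dependent variable.** With 30 trials and success probability π, the model mean is 30π. If the observed mean is p on the 0–1 scale, the fit gives π = p/30. With the link on π, a difference of 0.10 becomes 0.10/30 = 0.0033.

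A check on simulated data (4,000 persons, 30 days, true difference 0.10, baseline covariate, no random effect) gave:

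| Dependent variable, 30 trials | Coefficient | SE | z |
|---|---|---|---|
| Count of days | 0.1022 | 0.0028 | 36.4 |
| 0–1 proportion | 0.00341 | 0.00072 | 4.7 |

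The ratio of coefficients is 29.99, and exactly 30.0 with treatment as the only predictor.

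**3. Why this is more than a change of units.** The coefficient shrinks 30-fold but the standard error only about 3.9-fold. The variance the model assumes for the 0–1 score is 30 × (p/30) × (1 − p/30) = p(1 − p/30). At p = 0.5 this is 0.5 × 0.9833 = 0.492, an SD of 0.70. Against an assumed SD of 0.33 the ratio is 0.70/0.33 = 2.1. Over the assumed range:

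- p = 0.3, SD 0.40: √(0.3 × 0.99) / 0.40 = 0.545/0.40 = 1.4
- p = 0.7, SD 0.25: √(0.7 × 0.9767) / 0.25 = 0.827/0.25 = 3.3

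A simulation with 25 users per arm (400 replicates, no random effect) agrees: after multiplying by 30 the standard error was 0.207, against 0.095 for a linear analysis of the same data, a ratio of 2.2.

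**4. If the count is the dependent variable.** With the link on the probability, the coefficient is a difference in proportions (0.1022 above). On the expected-count scale the same fit gives 30 × 0.1022 = 3.07 days. The SAP does not say which of these is the adjusted mean difference.

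**5. What mixed scales would do to Cohen's d** (assumed baseline SD of the proportion 0.33):

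- proportion over SD of the proportion: 0.10/0.33 = 0.3
- the shrunken coefficient over SD of the proportion: 0.0033/0.33 = 0.01
- days over SD of the proportion: 3/0.33 = 9

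**6. Dependence on the link.** If the software applies the identity link to the mean count and not to the probability, the 30-fold shrinkage in step 2 does not occur. The variance in step 3 is still wrong for a 0–1 score, and a count would then give a coefficient in days. The documents do not say which convention applies.

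**The case against.** The strongest reply is that the SAP does not state that the 0–1 value is passed to the model. The code is headed as an example, `outcome` is a placeholder for every measure, and the scoring entry lists a numerator and a denominator, which is the events-and-trials pair that a 30-trial binomial model needs. Statisticians often call such an outcome a proportion. On that reading the pieces fit together: a count out of 30, a baseline proportion as covariate, and a coefficient that is a difference in proportions. This stands as a possible reading, so a 30-fold error is conditional and not demonstrated. It does not remove the conflict: the listed range is that of the quotient, the baseline is explicitly a proportion, and nothing in the SAP says that the count is used.

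A reader might also infer that the code comment that the margins contrast "should be the same as main effect of treat in above command" is wrong by a factor of 30 whichever scale is used. The documents do not support that. The code order appears disturbed: the only 12-week `margins` line sits under the linear `mixed` command, and the 24-week comment names `mixed` explicitly. For the linear model the equality is correct. For the binomial model, any gap comes from the scale on which `margins` predicts. It would arise equally with a correct count, and vanishes on the linear-predictor scale.

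Nor does the plan prescribe a Cohen's d of about 9. Section 5 divides the difference in an outcome by the SD of that same outcome, which implies one scale. The mismatch arises only if an analyst mixes the two, which the SAP fails to prevent but does not direct.

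Finally, the standard-error figures come from fits without a random effect, so they do not describe the planned two-timepoint mixed model.

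**Conclusion.** The SAP contradicts itself on the scale of this outcome: scored, described and baseline-adjusted as a 0–1 proportion, but coded with a model that requires a day count. If followed literally, with the link on the probability, the coefficient is 30 times too small. That factor depends on no assumed SD or sample size. The standard error is then also wrong; the 2.2-fold figure (1.4 to 3.3) and the d values of 0.01 and 9 are illustrations under assumed inputs. If the count is used, the model is coherent for the 30-day window, but the scale of the reported difference and of the SD for Cohen's d remains unspecified.

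The importance is minor to moderate: the point should be corrected before analysis, but it concerns example code for one secondary outcome, restricted to baseline cannabis users.

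**What to change.** Add one sentence to Section 5 (TLFB) and align the code with it. Either of two routes is enough:

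1. **Keep the binomial model.** State that the dependent variable is the count of days, with a denominator matching the recall window (30 or 90; the code now shows only 30). Report the treatment contrast as a difference in proportions, dividing any contrast in days by that denominator. Compute Cohen's d from this difference and the baseline SD of the proportion.
2. **Use the linear mixed model.** Fit the 0–1 proportion in the model already specified for the other outcomes and remove the exception in Section 5. Coefficient, margins, descriptive table and Cohen's d then share one scale. This changes the model and is an option, not a necessity.

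The same sentence should say whether using days or cannabis-free days are modelled. Appendix 2 derives the former and Section 5 names the latter, which reverses the sign of the effect. It would also help to place the equality comment directly under the command to which it refers.

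The cost is a sentence and a few lines of example code. No new data are needed and the primary analysis does not change.
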